6 STUDY DESIGN

6.1 Description

This pivotal study will be conducted where a minimum number of subjects will undergo a conventional urodynamic study (VUDS or non-VUDS) using the investigational device that will be conducted according to Good Urodynamic Practices (Rosier *et al.*, 2016). There is no need

for any repeat catheterization or urodynamics testing using an approved (non-investigational) urodynamics catheter. Urodynamic test results using the investigational device will be provided back to the referring physician for test interpretation. Given positive test results for the investigational device design verification and manufacturing process validation in accordance with ISO 13485, the sponsor has no reason to suspect device safety and performance will be any different as compared to the currently marketed T-DOC® 7 French catheter. Therefore, to reiterate, the urodynamics pressure data collected using the investigational device will be used in the referring physician’s test interpretation for each participant enrolled, unless there is reason to believe the test should be repeated. This can happen under normal (non-investigational) circumstances if the test was inconclusive (Abrams, 2006).

Further subject data collected will include age, medical history, height, weight, adverse events during or immediately following the test and 5-7 days follow-up, catheter insertion depth etc., as objective evidence on each patients CRF. There will be no control arm, blinding, or treatment/intervention component to this study.

In order to evaluate prospective product claims, a usability questionnaire will also be completed (one per clinical user, defined as an individual trained and certified to perform UDS). The study aim is to enlist 5 clinical users across 1-2 sites. Five users will allow for 85% of use errors to be detected (U.S. Department of Health and Human Services, 2016). A minimum of 1 physician should be utilized.

The following schematic diagram gives a high-level overview of the study design and subject flow-through:

Patients 12 years and younger are referred for Urodynamic testing

Patient and caregivers are approached to enrol in study at their Urodynamic visit and give informed consent & assent

A minimum of 10 male and 10 female patients will be recruited, with an overall minimum of 28 and maximum of 33

Telephone follow-up at 5-7 days post-procedure to assess any persistent symptoms following the Urodynamics test

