8.6 Device Accountability

All devices used directly for testing subjects must be recorded using the device LOT number on the subjects CRF form.

8.6.1 Laborie to Study Site:

All investigational devices or equipment transferred between Laborie and the study site must be recorded through the Inventory Control Form. This includes postal deliveries and any deliveries made in person by Laborie. Any equipment or devices that are not used and are returned to Laborie must be recorded on the Inventory Control Log Template as well. When the devices have been received by Laborie, it is their responsibility to ensure that all inventory both at Laborie and the study site correlate. All investigational device accountability will be recorded through the Inventory Control Form.

8.6.2 Study Site Usage:

All devices used directly for testing subject samples must be recorded on the Inventory Control Form. All devices used by the study site that are not directly used for the testing of subject samples must be recorded on the Inventory Control Form. This includes any devices used for training or demonstration or any devices which are noted to be defective when opened.

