10 SUBJECT SAFETY

10.1 Definitions

10.1.1 Adverse Events:

Any untoward medical occurrence in a subject, whether or not related to the investigational medical device.

10.1.2 Adverse Device Effect:

Any adverse event related to the use of an investigation medical device.

10.1.3 Device Deficiency:

Inadequacy of a medical device with respect to its identity, quality, durability, reliability, safety or performance

10.1.4 Serious Adverse Event:

An adverse event that:

1. Led to a death;
2. Led to a serious deterioration in health of a subject, user, or others that:
 - a. Results in a life-threatening illness or injury;
 - b. Results in a permanent impairment of a body structure or body function;
 - c. Requires in subject hospitalization or prolongation of existing hospitalization;
 - d. Results in medical or surgical intervention to prevent life-threatening illness or injury or permanent impairment to body structure or a body function;
3. Led to foetal distress, foetal death or a congenital abnormality/birth defect.

10.1.5 Unanticipated Adverse Device Effect:

Any serious adverse effect on health or safety or any life-threatening problem or death caused by, or associated with, a device, if that effect, problem, or death was not previously identified in nature, severity, or degree of incidence in the investigation protocol or application, or any other unanticipated serious problem associated with a device that relates to the rights, safety, or welfare of subjects.

10.1.6 Unanticipated Serious Adverse Device Effect (USADE):

Serious adverse device effect which by nature, incidence, severity or outcome has not been identified in the current version of the risk analysis report.

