10.2 Data Collection

Adverse events, device deficiencies, serious adverse events, and unanticipated adverse device effect shall be recorded on the CRF.

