12.4 Sample Size Determination & Power

Sample size calculations were and will be performed in accordance with Binomial Distribution theory (except for the second exploratory objective), utilizing the following formula:

$$n = \frac{\ln(1 - \text{confidence level})}{\ln(\text{reliability})}$$

Where n is the number of samples (e.g., patients, clinicians), and \ln is natural log. In the case of the primary endpoint, the desired confidence level and reliability have been stated as 95% and 90% respectively. Hence the minimum required number of samples for the primary endpoint is 28 as shown below.

$$n = \frac{\ln(1-0.95)}{\ln(0.90)} = 28$$

In addition, the study sponsor will allow up to 33 subjects (20% additional) during the allowable recruitment time period given the minimum recruitment goals are met (see Section 6.1 for and Section 7.1 for stratification and recruitment requirements). The additional subjects will ensure that the desired confidence and reliability levels are met should any data or subjects be disqualified due to technical errors or if any subject requests to exit the study.

In the case of the secondary endpoint, the confidence level has been stated to be 80% and the reliability statement will be calculated based on the actual number of clinicians who respond to the questionnaire. For instance, if 5 clinicians respond to the questionnaire, and an $\alpha = 0.20$ (i.e., (1- confidence level)) is maintained, the reliability of this test will drop to approximately 73%.

In the case of the first exploratory endpoint, the confidence level has been stated to be 95% and the reliability statement will be calculated based on the actual number of subjects who respond to the questionnaire. For instance, if 14 subjects respond to the questionnaire, and an $\alpha = 0.05$ (i.e., (1- confidence level)) is maintained, the reliability of this test would be approximately 80%.

In all cases, test statistics will be calculated based on the actual number of samples achieved.

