12.6 Analysis Plan

All subjects enrolled will be considered in the final analysis. Data will be analysed as discussed in Section 12.1 above. A Statistical Analysis Plan containing the details of the analyses and hypothesis testing will be finalized prior to database lock.

If any CRFs are found to be incomplete, the study monitor will follow-up as to the reasoning why. If for some reason a clinical user is unable to complete their questionnaire, the questions they have completed will be included in the analysis. Data will be monitored as the study progresses, please refer to Section 7.7 for details about suspension or premature termination.

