Secondary	
To evaluate the usability of the device by collecting clinical user feedback and evaluating the following subjective measures using defined ordinal scales: ease of use, ease of insertion, presence of artefacts, stability of the tracing, perceived time savings, ease of voiding around catheter, presence of use errors and overall satisfaction.	The usability performance endpoint will be captured in a questionnaire format. The trained clinical users will rate the T-DOC® 5 Fr performance on a scale of 1-5 on the study outcome questionnaire.
Exploratory	
To explore whether the newly designed, smaller sized T-DOC® 5 Fr catheters causes undue discomfort based on subjective subject feedback regarding the discomfort and pain level, for those able to communicate such feedback.	This exploratory endpoint will be measured by collecting patient feedback (within the abilities of the child) regarding the level of discomfort and pain experienced during their Urodynamic test using the Wong-Baker visual analogue scale. Patients capable of providing feedback on a Visual Analogue Scale, will grade their discomfort/pain at 5 or lower, on the Wong-Baker scale from 0 ("No Hurt") to 10 ("Hurts worst").
To explore the effect of several factors (e.g., age, gender, weight, height) on optimal insertion depth of the T-DOC® 5 Fr catheters.	Subjects' age, gender, weight, and height will be recorded on TDOC5Fr-PEDS-01-CRF1. These data will be analysed to determine a subject stratification approach to be used in examining further hypotheses for later research regarding optimal insertion depth.

Analysis revisions from the protocol

All subjects enrolled and completed the urodynamic procedure will be considered in the final analysis. Enrolled subjects who do not undergo the urodynamic procedure or begin the urodynamic procedure but do not complete it (for any reason determined by the investigator to be unrelated to the T-DOC® 5 Fr catheters) will not be included in the final analysis and can be replaced.

Primary Endpoint

In the statistical analysis plan, the null hypotheses for the safety and effectiveness endpoints are designed to rule out success rates $\leq 75\%$. The hypotheses as stated in the protocol are based on obtaining a point estimate of $\geq 95\%$ rather than bounding the lowest rate that would be consistent with the observed data.

The allowable Type I error (α) for each hypothesis will be 5% (1-sided), and the Type II error is calculated to be 10% (90% power).

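### Protocol 12.4, protocol 12.6 and the SAP define different analysis sets, and a catheter failure that stops the test has no stated score, so it can leave the effectiveness denominator

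*Protocol*

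**What the plan says.** Three places bear on who is counted for effectiveness.

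- **Protocol 12.4 (Sample Size Determination & Power)** sets a minimum of 28 and a maximum of 33. The extra places are there "should any data or subjects be disqualified due to technical errors or if any subject requests to exit the study". Technical error is not defined, nobody is named to decide it, and nothing excepts a fault of the investigational catheter.
- **Protocol 12.6 (Analysis Plan)**: "All subjects enrolled will be considered in the final analysis". It leaves the details to the SAP.
- **SAP, Analysis revisions from the protocol**: "All subjects enrolled and completed the urodynamic procedure will be considered in the final analysis". Children who never undergo the procedure are excluded and may be replaced. So are children who start and do not finish, provided the investigator judges the reason unrelated to the T-DOC 5 Fr catheters. Both primary hypotheses in the SAP are then written for enrolled children who complete the procedure.

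Other sections touch on device failure without linking it to the endpoint.

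- Protocol 8.6.2 asks for the Inventory Control Form to list devices not used directly on subjects, among them "any devices which are noted to be defective when opened".
- Protocol 10.2 states: "Adverse events, device deficiencies, serious adverse events, and unanticipated adverse device effect shall be recorded on the CRF". Section 10.1.3 defines a deficiency as "Inadequacy of a medical device with respect to its identity, quality, durability, reliability, safety or performance".
- Protocol 6.1 says the pressure data go to the referring physician "unless there is reason to believe the test should be repeated".
- Protocol 13.3 leaves missing values missing and analyses observed values only.

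The effectiveness endpoint itself is one yes/no clinician rating per child (protocol 9.1; SAP, Study Objectives and Endpoints).

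**The concern.** The catheter's stated purpose is to measure urodynamic pressure (protocol 5.2). If it gives no usable signal and the test stops for that reason, this is the outcome the effectiveness endpoint should register. The plan does not make sure that it does.

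Under 12.4 such a case could be called a technical error and its place refilled. Under 12.6 the child is in the analysis. Under the SAP the child is not among those excluded, but is also not among the completers to whom the hypothesis refers. If no rating is recorded, 13.3 means that nothing is entered in its place.

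The study is unblinded (protocol 12.5). The one relatedness judgement the SAP does specify is made by the investigator, who can know how the test went. Any discretion that removes device failures from the denominator moves the observed rate in one direction, toward success, and with 28 to 33 children a single case can settle a primary hypothesis.

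**Working it through.** **The plan's own figures.**

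- Sample size, 12.4: n = ln(1 − 0.95)/ln(0.90) = 28.43. The plan states 28; rounding up would give 29. The maximum of 33 leaves 33 − 28 = 5 spare places.
- Decision rule, 12.1.2, against a rate of 95%: P(X ≤ 24 | n = 28) = 0.049 and P(X ≤ 25) = 0.163, so the stated cut between 24 and 25 reproduces.

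**Where a started test goes under each text.**

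| Situation | Protocol 12.4 | Protocol 12.6 | SAP |
|---|---|---|---|
| Stopped, cause unrelated to catheter | may be disqualified | counted | excluded, replaceable |
| Stopped, cause is the catheter | may be disqualified, since the term is undefined | counted | not excluded, but outside the hypotheses; no score |
| Completed and rated, tracing poor | data may be disqualified | counted | counted as rated |

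The second row is the gap. In the third row 12.4 conflicts with the other two texts.

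**Effect of one child under the SAP test.** Inputs: null 75% and one-sided 5% (SAP, Primary Endpoint); n from 28 to 33 (protocol 12.4). The SAP names no test, so the exact binomial is my assumption, in line with protocol 12.1. The p-value for s successes in n is P(X ≥ s | n, 0.75).

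- For n = 28: P(25) = 0.0385, P(26) = 0.0133, P(27) = 0.0030, P(28) = 0.0003.
- 25/28: the sum of all four is 0.055, a fail.
- 26/28: the sum of the last three is 0.017, a pass. The pass mark at n = 28 is therefore 26.

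A study that stops at 28 analysed children fails with 25/28. If one failure is dropped and the next child is a success, it stops at 26/28 and passes. That comparison includes an extra child. If the dropped child is kept as well, the count is 26/29, p = 0.046, which just passes. A comparison on the same children, without replacement, is cleaner:

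| Failure counted | Failure dropped |
|---|---|
| 25/28, p = 0.055, fails | 25/27, p = 0.021, passes |
| 29/33, p = 0.059, fails | 29/32, p = 0.025, passes |

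**Effect on the error rate.** Suppose 33 are enrolled, the true rate over all 33 is 75%, and up to k failures are dropped without replacement. The pass mark is recomputed for the number left.

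| k | 0 | 1 | 2 | 3 | 4 or 5 |
|---|---|---|---|---|---|
| Chance of passing | 2.1% | 5.9% | 13.2% | 24.7% | 39.4% |

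Alternatively, let a share f of failures be dropped and replaced until 28 are analysed. The apparent rate is q = 0.75/(0.75 + 0.25(1 − f)).

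| f | 0 | 10% | 20% | one third | one half |
|---|---|---|---|---|---|
| q | 0.750 | 0.769 | 0.789 | 0.818 | 0.857 |
| P(X ≥ 26, n = 28) | 1.7% | 2.8% | 4.7% | 9.4% | 21.6% |

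The second model ignores the cap of 33. Both k and f are assumptions; the documents give no expected rate of technical failure.

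**The case against.** The best defence is that 12.4 is a recruitment allowance and not an exclusion rule. It says what the spare places are for if something is disqualified. The equipment also includes a processor, software, cables and pump tubing (protocol 8.1), so a technical error need not be a catheter fault. Protocol 12.6 defers to the SAP, and the SAP protects against the obvious abuse: completed tests stay in, and an unfinished test leaves only when the cause is judged unrelated to the catheters. This stands as far as it goes. It does not supply a score for the unfinished test whose cause is the catheter, and it leaves the 12.4 wording in conflict with the SAP.

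Three stronger readings are tempting, and the documents do not support them.

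- *Defective catheters are recorded only on the inventory form.* Section 10.2 requires device deficiencies on the CRF, and the 10.1.3 definition covers quality, reliability and performance. The 8.6.2 sentence is accountability for units not used on a child.
- *A repeated test removes the child from the count.* It does not. The child stays in and the clinician still answers yes or no, possibly no. What is missing is a statement of which attempt is rated.
- *Device failures are scored as successes or left out by rule.* The documents are silent. They permit such failures to drop out; they do not require it.

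It is also fair to say that scoring every catheter exchange, or every unit found defective on opening, as not effective would replace the clinician rating that protocol 9.1 justifies with a composite. That is a debatable change of endpoint and is not needed to close the gap.

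**Conclusion.** The point holds as a gap in the definition of the analysis set and in the scoring of device failure. The three texts do not agree, and a catheter-caused failure to complete has no stated place in the effectiveness analysis. A reader might conclude that the primary result is biased; the documents show only that it could be, and that any such bias would run toward success.

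The size depends on how many failures are affected. One child is enough near the pass mark (25/28 against 26/28, or 29/33 against 29/32). For a device whose true rate is at the 75% null, dropping and replacing up to a fifth of failures at n = 28 keeps the chance of passing within the nominal 5%; a third or more does not. At 33 enrolled, dropping a single failure takes it to 5.9%. These figures assume an exact binomial test and assumed numbers or shares of dropped failures. The matter should be settled before database lock, but it does not show the design to be unsound.

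**What to change.** - **Protocol 12.4:** limit disqualification for technical errors to documented causes outside the T-DOC catheters, such as pump, cable or processor, so that it agrees with the SAP. Reconcile 12.6 with the same set.
- **SAP, analysis set and hypotheses:** include every child in whom the procedure was started with the T-DOC 5 Fr catheters. Score a non-completion or an uninterpretable pressure tracing as not effective unless a cause outside the T-DOC catheters is documented.
- **SAP, endpoint:** state that the clinician rating refers to the first attempt.
- **Reporting:** describe catheter exchanges, units defective on opening (already device deficiencies for the CRF under 10.2) and repeat tests, and add a sensitivity analysis that counts them as failures. The primary endpoint remains the clinician rating, apart from the scoring rule above.

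The cost is a few sentences in 12.4, 12.6 and the SAP, and perhaps some CRF fields; the CRFs are not among the documents, so these may already exist. The SAP allows revision before database lock. The observed effectiveness rate may come out slightly less favourable.

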12.5 Randomization / Blinding

Randomization and/or blinding is not utilized in this study based on study design.

12.6 Analysis Plan

All subjects enrolled will be considered in the final analysis. Data will be analysed as discussed in Section 12.1 above. A Statistical Analysis Plan containing the details of the analyses and hypothesis testing will be finalized prior to database lock.

If any CRFs are found to be incomplete, the study monitor will follow-up as to the reasoning why. If for some reason a clinical user is unable to complete their questionnaire, the questions they have completed will be included in the analysis. Data will be monitored as the study progresses, please refer to Section 7.7 for details about suspension or premature termination.

12.7 Deviations

In any event there are deviations from the original statistical plan they will be described and justified in the final report.

12.8 Early Stopping

An interim data analysis will be conducted once 30 subjects have been recruited in order to validate the product design meets the user requirements.

There are currently no criteria for stopping the study early on statistical grounds, however please refer to Section 7.7 for details about suspension or premature termination.

13 DATA HANDLING & RECORD KEEPING

13.1 Direct Access

The Investigator/Institution will permit trial-related monitoring, audits, IRB review, and regulatory inspections by providing direct access to the source data/documents as needed.

13.2 Confidentiality & Security

All information disclosed or provided by the Sponsor (or any company/institution acting on their behalf), or produced during the study, including, but not limited to, the Study Protocol, the CRFs, the Instructions for Use and the results obtained during the course of the study, is confidential. The Investigator or any person under his/her authority agrees to undertake to keep confidential and not to disclose the information to any third party without the prior written approval of the Sponsor.

However, the submission of this Study Protocol and other necessary documentation to the Ethics Committee (IRB) is expressly permitted, the IRB members having the same obligation of confidentiality.

The Sub-Investigators, if employed, shall be bound by the same obligation as the Investigator. The Investigator shall inform the Sub-Investigators of the confidential nature of the Usability Study.

The Investigator and the Sub-Investigators shall use the information solely for the purposes of the Study, to the exclusion of any use for their own or for a third party's account.

All data to Laborie will be confidential and all subject identifiers will be blacked out before being sent to Laborie. Documents will be kept in a secure location and all digital information will be kept following HIPAA and local government regulations.

13.3 Data Handling

A list of individuals will be maintained who are authorized to make any changes to the data. Data will be reviewed by the Sponsor (outside of monitoring personnel), and requests for clarification and/or corrections will be made through the monitor. Once the review is conducted, the database will be considered clean and ready for analysis. Missing values will remain missing, i.e. no attempt will be made to input missing values and only observed values will be used in data analyses and presentations.

13.4 Case Report Form (CRF) & Source Documents

All study staff will be trained on the protocol requirements and questionnaire completion. It is the responsibility of the Investigator to maintain adequate and accurate questionnaires and CRFs designed by Laborie to record all observations and other data pertinent to the clinical investigation. All questionnaires and CRFs should be completed in their entirety in a neat, legible manner to ensure accurate integration of data. Should a correction be made, the information to be modified must not be overwritten. The corrected information will be transcribed by the authorized person on the questionnaire. Source document worksheets for recording data will be created as agreed upon by the sponsor or the site as required. Data from the source documents should be entered into the CRF after each subject's visit. The anonymized urodynamic data files (DTA files) are requested by the sponsor for each patient, to confirm the quality of the tracing. A unique subject code will be assigned to each subject based on the site number (100) and sequential subject number (i.e. 100-001). The investigator is responsible for maintaining subject identifying information. CRF's will be treated as source data in the event that the original information is entered in the CRF first (and no source document worksheet is utilized for that data point).

